3.3. Data collection and quality control

After a routine standard physical examination on the first day of life, all newborns will be examined by hip ultrasound. The standardized and uniform system of Graf will be used for diagnostics.²² The hip ultrasound examination will be performed by a trained and experienced neonatologist using an ultrasound machines (GE Logiq series) with a linear array transducer operating on an ultrasound frequency of 7–10 MHz. A Sonofirst® holding cradle and transducer fixation unit (Orthopunkt, Solothurn) will be used to prevent tilting errors and to standardize examination techniques.^{14,22} A web-based, password-protected tool, “HipScreen” (WebWaren, Bern, Switzerland)¹⁴ will be used for quality control purpose. The tool enables the screener to upload DICOM files exported from the ultrasound machines. Four images (two per hip side; one of them with measured alpha and beta angles according to Graf), will be required. This will allow continuous and reliable review of hip grading, diagnosis of DDH, and treatment decisions. Trained, on-site experts will check all examinations and promptly send comments to the screener. Discrepancies between expert assessments will be resolved by discussion and consensus.

After identification of all term newborns with Graf Type 2a cases (physiologically immature) of the neonatologist/data collector will be listed and the newborns and their mothers will be undergoing the screening process by research assistants to see whether they meet the inclusion criteria. The parents of the physiologically immature cases will be given oral information about hip dysplasia and study purpose. Consequently, parents will give their oral consent to participate. Those who refuse consent will be registered, but will not be included.

After the randomization of eligible newborns with physiologically immature (Graf Type 2a) hips, the research assistants will explain and give detailed information about the study again to the parents in both “swaddled” and “non-swaddled” groups. The parents will be requested to sign an informed consent form if they agree to take part in the study before they are given an ID number. After the obtaining the written consent form, a brief questionnaire about demographic (e.g. birth date, gender of newborn etc.) and birth related information such as fetal position, birth weight, number of parity and family history of DDH will be filled by the research assistants.

For babies assigned to the “swaddling” group, parents will be instructed to follow a pattern of traditional Mongolian swaddling as described above. For babies assigned to the “non-swaddling” group, parents will be instructed to do not swaddle at all and only use a wide sleeping bag with free leg position.

Trained research assistants will make home visits on weekly basis until the infants are 4-6 weeks of age to check and monitor the compliance of the families by observing the baby during every home visit and collecting retrospectively 24-hour diaries of swaddling and non-swaddling patterns. Also unscheduled visits from monitoring research assistants will be organized to estimate unreported non-compliance conducted for all families 2 to 3 times.

At 4-6 weeks follow up visit, the babies will be checked by Graf’s method of hip ultrasound performed by a trained radiologist uninformed about the initial status of the hips. Regardless of the study group, monthly controls will be fixed until complete maturation to Graf type 1 is documented. Families, who did not show up for follow-up will be contacted by phone or home

visit. In cases when the parents will not be able/willing to come to the follow-up control visit(s), the PI will visit the family and make the follow-up ultrasound examination at their home using a portable ultrasound device (MicroUs EXT-1H, REV:C). All infants in need of therapy (Graf type 2a-, 2c or worse) will be treated with Tubinger orthosis.

Monitoring: In the non-swaddling group, it is expected that some families would not adhere to their instructions of not swaddling because of grandparents/cultural pressures. To monitor compliance and obtain a measure of exposure, multiple sources of information will be used:

1. A retrospective 24-hour history of swaddling/clothing: will be recorded by research assistants during each weekly home visit through recording the carer's descriptions of the style of dress/clothing/ swaddling and length of each during the past 24-hour within the 24-hour retrospective diaries (a kind of behaviour diary adapted to record swaddling/clothing pattern)
2. Direct observation of research assistants during weekly visits: of the dressing/clothing/ swaddling of each child and discreetly recording observations of the type of baby clothing items that each family washed and hung to dry on the day of visit (available for observation during the majority of visits)
3. Analysis of the 7-days prospective mother's diaries used for sleeping and crying/fussing outcome measure: as mother's own reported behaviour during 2 time periods
4. Unscheduled visits from a monitoring research assistants: in order to estimate unreported non-compliance conducted for all families 1 to 3 times
5. End-study research assistant impressions' questionnaire: of their impression about compliance in each family and the consistency and extent of accuracy of the reports from each family during each week of child's life

For analysis, the first and third methods of exposure recordings above will be quantifiable and will be combined to reveal exposure to swaddling per child for use in per-protocol analysis. The other three methods detailed above will be triangulated with the data from the diaries.

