3. Willing to give informed consent
4. Newborns without any symptoms and complaint

Predefined exclusion criteria will be:

1. Newborns with obvious congenital abnormalities (with clear medical consequences)
2. Newborns with needs for intensive care treatment
3. Newborns with low (2499g or less)
4. Newborns with confirmed non-type 2a hips

Randomization sequence will be created using Excel 2007 (Microsoft, Redmond, WA, USA) with a 1:1 allocation using random block sizes of 4 by an independent researcher with no clinical involvement in the trial. After obtaining the consent from the parents, details of the allocated group will be given on colored cards contained in sequentially numbered and sealed envelopes. These will be prepared by the principal investigator and kept in an agreed location on the post-delivery ward. Randomization will take place before discharge when the data collector/neonatologist gives detailed consultation on usual postnatal care of newborns. Corresponding envelopes will be opened

only after the enrolled newborns completed all baseline assessments and it is time to allocate the intervention. Whereas parents allocated to the swaddling group and the research assistants will be aware of the allocated arm, the outcome assessor/radiologist will be kept blinded to the allocation.

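### Sections 3.2 and 3.3 give conflicting orders for consent, baseline data and allocation; under 3.3 a family can decline after randomization and have no trial data

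*Protocol*

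**What the plan says.** Protocol section 3.2 puts consent ahead of disclosure: "After obtaining the consent from the parents, details of the allocated group will be given on colored cards". It adds that envelopes are opened "only after the enrolled newborns completed all baseline assessments and it is time to allocate the intervention". The same section says that the research assistants know the allocated arm.

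Protocol section 3.3 describes a different sequence. Parents first receive oral information: "Consequently, parents will give their oral consent to participate". Those who refuse at this step are registered and not included. Then: "After the randomization of eligible newborns with physiologically immature (Graf Type 2a) hips, the research assistants will explain and give detailed information", and this goes to parents in both the swaddled and the non-swaddled group. Only now comes the signature, which is optional: "The parents will be requested to sign an informed consent form if they agree to take part in the study". The ID number is issued only after that. The questionnaire on demographic and birth-related items, including fetal position, parity and family history, is filled in by the research assistants after the written form is obtained.

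Section 3.5 promises an intention-to-treat analysis. It does not mention families who were randomized but did not sign.

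**The concern.** Randomization protects the comparison only if the decision to take part is made before the arm can be known. In section 3.3, full information, written agreement and the ID all come after randomization, at a time when parents are described by group. A family that dislikes its arm can simply not sign. Willingness to consent is also an inclusion criterion, so site staff could treat such a family as never eligible.

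If such refusals are more common in one arm, the infants left in the two arms are no longer comparable, and a larger sample does not cure that. The protocol makes a difference between arms plausible, because in the non-swaddling group "it is expected that some families would not adhere to their instructions of not swaddling because of grandparents/cultural pressures".

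A second, smaller issue is that questionnaire items used for balance checks, and possibly for adjustment, would be recorded by staff who know the arm. Family history of hip dysplasia is the item most open to this.

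**Working it through.** **1. The two sequences side by side**

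| Step | Section 3.2 | Section 3.3 |
|---|---|---|
| Consent before allocation | Consent, type not stated | Oral only |
| Detailed information | Not placed | After randomization, to both named groups |
| Written consent | Not separately placed | After randomization, optional |
| Enrolment / ID number | Enrolled before the envelope is opened | ID after written consent, so after randomization |
| Baseline data | All complete before the envelope is opened | Questionnaire after written consent, so after randomization |

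**2. Does reading the consent in 3.2 as the oral one reconcile them?** No. Section 3.2 still requires enrolment and every baseline assessment before the envelope is opened. Section 3.3 puts the ID and the questionnaire after randomization. Staff cannot naturally follow both.

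**3. What happens to a family that declines at the signature?** Under 3.3 it gets no ID, no questionnaire and no trial follow-up. Registration of refusals is stated only for the earlier oral step. The screening ultrasound exists, because it precedes eligibility, but no outcome would be collected for the trial.

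**4. How large could the effect be?** The inputs from section 3.2 are risks of 10% (non-swaddled) and 40% (swaddled), two-sided 5%, 80% power, about 40 per group and 20% dropout. The plan's own figure reproduces: 7.9 × (0.1×0.9 + 0.4×0.6) / 0.3² = 28.97, rounded up to 29 per group. No figure in the plan is in dispute here.

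The rest is assumption, since the protocol gives no refusal rate. Let r be the share of the non-swaddling arm that declines after allocation, p the risk over all infants allocated to that arm, and k the decliners' risk as a multiple of p. The risk among those who stay is p(1 − rk)/(1 − r). With p = 0.10:

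| r | k = 0.5 | k = 2 |
|---|---|---|
| 10% | 0.10×0.95/0.90 = 10.6% | 0.10×0.80/0.90 = 8.9% |
| 20% | 0.10×0.90/0.80 = 11.25% | 0.10×0.60/0.80 = 7.5% |
| 30% | 0.10×0.85/0.70 = 12.1% | 0.10×0.40/0.70 = 5.7% |

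Against an unchanged 40% in the other arm, r = 20% gives an apparent difference of 28.75 to 32.5 points where the true one is 30. Selection can also create a difference where there is none. If the risk were 25% in both arms (assumed), r = 20% gives 0.25×0.90/0.80 = 28.1% or 0.25×0.60/0.80 = 18.75% in the depleted arm, which is 3.1 points too high or 6.25 too low.

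**5. Power.** Take 40 randomized per arm and 20% later dropout (32 left per arm), with the pooled normal-approximation test of 10% against 40%. Power is 0.81 with no refusal, and 0.78, 0.75 and 0.71 with 10%, 20% and 30% refusal in the non-swaddling arm only.

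**The case against.** The two sections might be reconciled. Section 3.3 does not say that the envelope is open when parents sign, and arm-specific instructions appear only after the questionnaire. Randomization could mean assignment of a number, with the envelope opened later. This is possible, but it strains the text: 3.3 already speaks of parents in two named groups, and says that the explanation follows randomization. It is at least an ambiguity on a step where none should be left.

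The baseline conflict is narrower than it first looks. Hip type and alpha angle come from the screening ultrasound, before consent. Most questionnaire items (birth date, sex, birth weight, fetal position, parity) are fixed facts. That stands, and leaves family history as the main exposed item.

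The exact intention-to-treat set is often left to an analysis plan, and none is shown. That is fair for the definition, but no analysis plan can recover outcomes that were never collected.

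Four stronger readings are tempting and not supported:

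- A reader might infer that these families would vanish without trace. Envelopes are numbered sequentially, refusals are registered at the oral step, and the annexed trial profile is not shown, so a gap in the count may be visible. A count still supplies no outcome.
- A reader might infer that the protocol predicts refusal in the non-swaddling arm. The sentence on cultural pressure concerns adherence among enrolled families. It makes refusal by arm plausible, no more.
- A reader might infer that the analysis becomes close to as-treated. It does not: decliners would be missing, not moved to the other arm.
- A reader might measure the bias by supposing that 10–20% decline and swaddle at 40% risk, so that the arm's risk is 0.10 + 0.30 × 0.10 = 13% to 0.10 + 0.30 × 0.20 = 16%, and the difference 27 to 24 points instead of 30. The arithmetic is right, but it shows dilution by crossover, not selection.

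**Conclusion.** The concern holds as a contradiction in trial conduct with a real route to bias. The two sections cannot both be followed on their natural reading, and following 3.3 as written lets families leave after allocation with no questionnaire or outcome data. Whether that biases the result depends on refusal differing by arm and on decliners differing in prognosis.

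The documents quantify neither, so size and direction are unknown, and refusal in the swaddling arm is also possible. Under the assumed ranges above, the shift in the non-swaddling arm at the planned 10% risk runs from 2.1 points too high to 4.3 points too low. For scale, the standard error of the planned difference with 40 per arm is √[(0.09 + 0.24)/40] = 9.1 points. So at the planned risks the shift would be modest beside sampling error, but unlike sampling error it is systematic. The effect on covariates is limited mainly to family history.

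**What to change.** State one order in both 3.2 and 3.3: eligibility confirmed, full information given, written consent signed, ID number issued, baseline questionnaire completed, and only then the next envelope opened. Add that every infant whose envelope was opened is counted and analysed in the allocated group, including families who later decline the allocated care. A family that withdraws permission to use its data is counted by arm with its outcome missing.

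If any infants have already been randomized under the 3.3 order, report envelopes opened and IDs issued for each arm.

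The cost is protocol wording and the order of forms on the ward, with no added staff, visits or sample size. The downside is that some families will decline before randomization instead of after it, so slightly more families may have to be approached. Type 2a infants are already followed monthly by ultrasound under the national guideline (section 1), so outcomes for families who sign and then decline the allocated care should be obtainable.

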TRADITIONAL MONGOLIAN SWADDLING AND DEVELOPMENTAL DYSPLASIA OF THE HIP: A RANDOMIZED CONTROLLED TRIAL

RESEARCH PROTOCOL

[name] and SMOPP team
National Center for Maternal and Child Health, Mongolia
29 June, 2019

SUMMARY

Background

In Mongolia, swaddling is an ancient practice and nowadays it still remains common child care in the first months of life. Mongolian traditional way of swaddling technique involves tight, prolonged wrapping from the head or neck down in two to three layers of thin cotton cloth, covered by layers of thick blankets and binding with 2-3 tiers for whole day. This traditional prolonged swaddling where arms and legs are extended and hips are in adduction position might increase the risk for developmental dysplasia of the hip (DDH). DDH is a major health problem that can lead to lifelong disability if diagnosis is missed in first weeks of life. Mongolia is the first Asian country that launched a universal ultrasound hip screening (Graf's method) for DDH in newborns. All DDH cases are followed up on monthly basis by hip ultrasound and treated with a simple extension and abduction orthosis if necessary.

Objectives

To test the effect of traditional swaddling on the DDH in Mongolia

Design

A prospective, randomized trial with two study groups will be conducted in Mongolia. The term newborns with Graf Type 2a (physiologically immature) will be randomly allocated to one of two groups. The intervention/"non-swaddling" group will be instructed not to swaddle at all. The control/"swaddling group" will be swaddled in the common traditional Mongolian method. Both groups will be followed up by Graf's method of hip ultrasound at 4-6 weeks' intervals until healing according to Mongolian national guideline. All infants in need of therapy (Graf type 2a-, 2c or worse) will be treated with Tubinger orthosis. At around 12 months of age all children will be checked again by Graf's method of hip ultrasound.

Timeline and Analysis

The study will be conducted between August 2019-March 2021. Findings will be reported in March-June 2021. Analysis will be intention to treat.

Ethics

The study protocol will be reviewed and approved by the Institutional Review Board at the National Center for Maternal and Child Health and the Ethical Review Committee of Ministry of Health, Mongolia prior to start the study.

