2. OBJECTIVES

Mongolian traditional prolonged swaddling where arms and legs are extended and hips are in adduction position increases the risk for DDH. This hypothesis is going to be tested in this study.

The primary outcomes: The number of “non-Type 1” hip cases at the monthly follow-up ultrasound control visits

The secondary outcomes:

- a. number of DDH cases (Graf Type 2a-, Type C, D and Type 4) at any monthly follow-up ultrasound control visits and rim defects at 12 months’ follow-up
- b. correlation between the primary outcome and the swaddling frequency (in hours per day) and swaddling duration (in days)
- c. primary and secondary outcomes association with the swaddling.

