3.4. Outcome assessments

The primary outcome of the study will be the number of “non-Type 1” hip cases at the any monthly follow-up ultrasound control visits.

The secondary outcomes are:

- a. number of DDH cases (Graf Type 2a-, Type C, D and Type 4) at any monthly follow-up ultrasound control visits
- b. correlation between the primary outcome and the swaddling frequency (in hours) per day and swaddling duration in days
- c. primary and secondary outcomes association with the swaddling.

Operational definitions

Swaddled: Newborns are swaddled in the common traditional Mongolian method at least 20 hours per day for 4-6 weeks

Non swaddled: Newborns are not swaddled at all.

The “non-Type 1” hip case: a neonate who’s Graf ultrasound type is other than Type 1 at any monthly follow-up visits

Physiologically immature or Graf Type 2a hip: has a certain degree of physiological delay in ossification of the bony acetabular roof. The alpha angle is between 50 and 59, the beta angle is between 55 and 77, and the patient is younger than 6 weeks of age.

Graf Types 2a- and 2a+: Starting from 55° alpha at 6 weeks of age and assuming a spontaneous maturation of 1° per week. Type 2a+ is still considered to be physiological while 2a- hips are assigned to the group of DDH.

Swaddling hours: according to the 24-hour diaries of swaddling and non-swaddling patterns of mothers and research assistants' compliance check reports

Swaddling days: according to the 24-hour diaries of swaddling and non-swaddling patterns of mothers and research assistants' compliance check reports

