4. DURATION OF PROJECT

Data collection will start since September 2019 to March 2021. Another 3 months for data management and analysis and another 3 months for report writing are required. Therefore the total duration of the project is 18-24 months. The writing and publication of scientific papers may continue after this.

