Annex 4. Data analysis plan

Table 1. Baseline characteristics of participants

Characteristics	Non-swaddling	Swaddling	P value*
	N= n(%)	N= n(%)	
Mean age in days at screening (mean ±sd)			
Girls			
Breech position			
Family history of DDH			
Birth weight >4000			
Firstborn baby			
Mean of Graf hip alpha angle at initial screening (mean ±sd)			
Swaddling days			
Swaddling hours per day in			

sd-indicates standard deviation, *DDH* indicates Developmental Dysplasia of the Hip

**chi*² or χ^2 test

Table 2. The associations between the main outcomes and the intervention analyzed by univariate analysis (*chi*² or χ^2 test)

Characteristics	Control	Intervention	OR	P value
	n/N (%)	n/N (%)		
Mean age in days at screening				
Girls				
Breech position				
Family history of DDH				
Birth weight >4000				
Firstborn baby				
Mean of Graf hip alpha angle at initial screening				
None-Type 1 hips				
DDH				
Rim defects at follow-ups				

Table 3. The associations between the main outcomes and the intervention analyzed by multiple logistic model

	Control n/N (%)	Intervention n/N (%)	Adjusted OR*	P
Primary outcome				
None-Type 1				
Secondary outcome				
DDH				
Rim defect				

DDH indicates Developmental dysplasia of the hip, OR indicates odds ratio

**Will be adjusted for significant baseline variables*

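### Rim defects at 12 months are a named secondary outcome, but sections 3.3 and 3.4 omit the 12-month scan, the annex table gives no time point, and no enrolment close protects the scan

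*Protocol*

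**What the plan says.** Two places in the protocol plan the late scan. The Summary, under Design, first describes ultrasound follow-up until healing and then adds "At around 12 months of age all children will be checked again". Section 2 (Objectives) includes "rim defects at 12 months" in secondary outcome a.

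Two places leave it out. Section 3.3 sets a scan at 4-6 weeks and then says "monthly controls will be fixed until complete maturation to Graf type 1 is documented". It describes no later visit. Section 3.4 gives secondary outcome a as "number of DDH cases (Graf Type 2a-, Type C, D and Type 4) at any monthly follow-up ultrasound control visits", with neither rim defects nor 12 months.

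The analysis tables bring the outcome back without fixing its timing. Annex 4, Table 2 has a row "Rim defects at follow-ups", and Table 3 has a rim-defect row with no time point.

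On dates, section 4 says "Data collection will start since September 2019 to March 2021", and section 3.2 gives the same window. No enrolment period or last enrolment date is stated. The Summary adds "Findings will be reported in March-June 2021", directly after data collection ends, while section 4 allows three months for data management and analysis and three more for writing.

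**The concern.** The 12-month scan is the plan's only check, common to all infants, on whether hips classed as Type 1 in the first weeks are still normal later. Two things put it at risk.

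First, the sections that staff work from do not contain it. The national routine described in section 1 also follows Type 2a hips only until they mature, so usual care would not fill the gap. If rim defects were then counted at whatever visits took place, the number of scans per infant would depend on hip status. The trial's hypothesis is that hip status depends on arm. An outcome looked for more often in one arm can show a difference that partly reflects the looking.

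Second, a scan at 12 months has to fit inside data collection. With no enrolment close, nothing in the plan ensures that it does for infants recruited later.

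**Working it through.** **Setting the passages side by side**

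| Place | 12-month scan or visit | Rim defects |
|---|---|---|
| Summary, Design | yes, all children | not named |
| Section 2, outcome a | yes | yes |
| Section 3.3, procedure | absent | absent |
| Section 3.4, outcome a | absent | absent |
| Annex 4, Tables 2 and 3 | no time point | yes |

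The named outcome therefore stands in section 2 and in the tables, and is missing from the procedure and from the restated outcome list.

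**Direction of unequal detection.** Section 3.2 assumes non-Type 1 hips in 10% of the non-swaddled and 40% of the swaddled group. Under section 3.3 an infant whose hips are Type 1 has no further monthly control, and an infant whose hips are not Type 1 has at least one more. Counted over all visits, the swaddling arm would have more scans at which a rim defect could be recorded. The direction follows from the plan. The size does not.

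**Enrolment window.** The protocol states no last enrolment date, so there is no figure of its own to reproduce here.
- From 1 September 2019 to the start or end of March 2021 is 18.0 to 19.0 months.
- Infants are enrolled in the first days of life, so enrolment date is close to birth date.
- For a scan at 12 months: 18.0 - 12 = 6.0 and 19.0 - 12 = 7.0 months of enrolment, ending about March 2020.
- If a scan at 10 months counts as around 12: 8.0 to 9.0 months.

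**Supply of infants.** From sections 1 and 3.2: about 11,000 births a year, one of 6 screeners recruiting, 10-15% Type 2a, about 40 per group (80 in all). Equal load across the 6 screeners is an assumption.
- 11,000 / 6 x 0.10 = 183 a year, or 15.3 a month.
- 11,000 / 6 x 0.15 = 275 a year, or 22.9 a month.
- These counts are before the other eligibility criteria.

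**Share enrolled too late.** Months to reach 80 = 80 / (monthly supply x share enrolled). Share too late = 1 - window / months, or zero if enrolment finishes inside the window. Uniform accrual is assumed. The 50% and 30% enrolment shares are assumptions, not protocol figures.

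| Share enrolled | Months to 80 | Too late, 6-month window | Too late, 7-month window |
|---|---|---|---|
| 100% | 3.5-5.2 | 0 | 0 |
| 50% | 7.0-10.5 | 14-43% | 0-33% |
| 30% | 11.6-17.5 | 48-66% | 40-60% |

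Example: at 50% and the lower supply, 80 / (15.3 x 0.5) = 10.5 months, and 1 - 6/10.5 = 43%. Over both windows the ranges are about 0-43% at 50% enrolment and about 40-66% at 30%. With the 8-9 month window, the 50% range falls to about 0-24%. Section 3.2 also lists 6 further screeners in the preterm unit. If births were shared over all 12, supply would halve and full enrolment would itself take 7.0-10.5 months.

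**Balance of that loss.** Section 3.2 randomises 1:1 in blocks of 4. At any point in the sequence the arms can differ by at most two infants, so a calendar cut-off removes nearly equal numbers from each arm.

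**The case against.** The strongest reply is that the plan contains no real conflict. The sentence in section 3.3 limits the monthly series only, and the Summary gives the two steps in order: follow-up until healing, then a check of all children. Section 2 supplies the time point that the table row lacks. The trial has one centre, whose staff also have the Summary and Objectives. This stands in part. A reader might infer that section 3.3 ends all follow-up at Type 1 and so overrules the Summary; the text does not say that. What remains is an omission from the procedure, a second version of outcome a in section 3.4 that differs from section 2, and a table label that can be read over several visits.

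A reader might also infer from the 10% and 40% rates that rim defects would be looked for four times as often in the swaddling arm, giving a fourfold spurious excess. The documents do not support that. The rates are sample-size assumptions for the primary outcome, which section 3.4 defines over any monthly visit, so they are not tied to the first scan. The inference also needs rim-defect risk to be unrelated to early hip type, which nothing in the protocol states. And if section 3.3 alone were followed, infants with early non-Type 1 hips would also leave follow-up on maturing, so a true 12-month outcome would be largely missing in both arms.

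On the calendar, the reply is that the protocol's own figures allow 80 infants well before March 2020. That is correct at full enrolment under equal screener load. The loss is conditional on slower accrual, and being nearly balanced by arm it is not selection by hip status.

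**Conclusion.** The point holds as an inconsistency about a named secondary outcome, together with a calendar that does not secure it. The primary outcome is not affected.

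Unequal detection by arm is possible, and its direction would favour the trial's hypothesis of harm. It arises only if staff follow sections 3.3 and 3.4 alone or if the rim-defect row is counted over all visits. Its size cannot be derived from the documents.

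The calendar limit of about March 2020 for birth is plain arithmetic. The resulting loss runs from none at full enrolment, through about 0-43% at 50%, to about 40-66% at 30%, given equal load over 6 screeners and uniform accrual. It would mainly cost precision and completeness. The difference between the reporting dates in the Summary and section 4 is administrative, and matters here only because reporting from March 2021 leaves no room for later 12-month scans.

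**What to change.** Reconcile the passages, using what the Summary and section 2 already plan:

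- In section 3.3, add the 12-month ultrasound for every randomised infant, including those already documented as Type 1. The monthly-control rule can stay as it is.
- In section 3.4, restore rim defects at 12 months to secondary outcome a, so that it matches section 2.
- In Annex 4, label the rim-defect rows of Tables 2 and 3 as referring to the 12-month scan, so that both arms are assessed at one common time point.
- Either close enrolment at least 12 months before data collection ends, or run data collection until the last infant's 12-month scan. Report this outcome only after that, and bring the dates in the Summary and section 4 into line.

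No procedure is added beyond what the protocol already plans. The cost is protocol wording and possibly later reporting of this secondary outcome.

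### The principal investigator prepares the allocation envelopes and also does the home follow-up scans, so the stated blinding of the outcome assessor is not secured for home-scanned infants

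*Protocol*

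**What the plan says.** Section 3.2 has the randomization sequence created "by an independent researcher with no clinical involvement in the trial". It then says that "details of the allocated group will be given on colored cards contained in sequentially numbered and sealed envelopes", and of the envelopes: "These will be prepared by the principal investigator and kept in an agreed location on the post-delivery ward". The same section states that "the outcome assessor/radiologist will be kept blinded to the allocation", with no exception.

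Section 3.3 has the 4–6 week scan "performed by a trained radiologist uninformed about the initial status of the hips". If parents do not attend after being contacted, "the PI will visit the family and make the follow-up ultrasound examination at their home using a portable ultrasound device".

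Section 3.4 defines a case for the primary outcome as a Graf type other than Type 1 at any monthly follow-up visit. It does not set home scans apart.

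On image review, Section 3.3 describes the HipScreen platform as a quality-control tool: "The tool enables the screener to upload DICOM files exported from the ultrasound machines", and on-site experts check examinations and send comments back. Section 3.5 says that all ultrasound pictures are uploaded.

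**The concern.** For a home-scanned infant the principal investigator is the outcome assessor. That person has handled the group cards, supervises the study forms, and scans in a home that has received arm-specific bedding or clothing. The blinding statement in Section 3.2 covers this assessor by its wording, but no procedure in the protocol makes it true.

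The outcome depends on an angle measured by the operator. Section 1 gives 60° alpha as the threshold, and Section 3.4 puts Type 2a at 50 to 59. Every infant enters as Type 2a, so many follow-up readings may lie close to the cut. Section 6 states the expected direction, namely that swaddling harms these hips. An assessor who knows the arm could, without intending to, shift borderline readings that way. The infants concerned are not a random subset either, since home scans go to non-attenders and non-attendance may differ by arm.

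**Working it through.** **1. Roles side by side**

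| Step | Who | Section |
|---|---|---|
| Creates sequence | Independent researcher | 3.2 |
| Prepares numbered envelopes | Principal investigator | 3.2 |
| Checks eligibility, takes written consent | Research assistants | 3.3 |
| Gives the pre-discharge consultation at which randomization takes place | Data collector/neonatologist | 3.2 |
| Scans at clinic follow-up | Radiologist, stated blinded | 3.2, 3.3 |
| Scans at home follow-up | Principal investigator, blinding not addressed | 3.3 |

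**2. Can the principal investigator know an infant's arm?** Preparing the envelopes shows which arm each envelope number carries. Identifying an infant's arm also needs the link from envelope to infant, or a cue in the home.
- Link: nothing withholds it. Section 7 keeps all completed study forms under the principal investigator's direct supervision.
- Cue: Section 3.1 supplies warm clothing and sleeping bags to one arm, and a blanket and cotton sheets to the other. Section 3.3 itself relies on research assistants reading exposure from the infant's dress and the washing seen at home.

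**3. Which home scans matter?** Monthly controls stop once Type 1 is documented (Section 3.3), and a case is non-Type 1 at any monthly visit (Section 3.4). An infant who is non-Type 1 at the first follow-up scan is already a case. One who is Type 1 leaves monthly follow-up. The first follow-up scan therefore settles the primary outcome. It falls at 4–6 weeks, as the assigned practice ends, when cues in the home are likely to be strongest. Later home scans can still affect the secondary DDH outcome.

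**4. Size.** The protocol gives no figure for home scans, so there is none to reproduce. Its sample size does reproduce with the rates used in its worked line: 7.9 × (0.1×0.9 + 0.4×0.6) / 0.3² = 28.97, so 29 per group, raised to about 40.

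The illustration below rests on assumptions that are not in the protocol: 40 per arm, no true effect, and a common true rate p. A share h of each arm has its deciding scan at home. A fraction e of those readings moves towards the hypothesis (Type 1 to non-Type 1 if swaddled, the reverse if not).

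- Swaddled: p_s = p + h·e·(1 − p)
- Non-swaddled: p_n = p − h·e·p
- Spurious difference: d = p_s − p_n = h·e
- Rejection rate of a nominal two-sided 5% test: Φ((d − 1.96·s0)/s1) + Φ((−d − 1.96·s0)/s1), where s0 and s1 are the pooled and unpooled standard errors

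Example with p = 0.10, h = 0.20, e = 0.25: p_s = 0.145, p_n = 0.095, d = 0.05. The rejection rate is 10.5%.

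| h | e | d | Rejection, p = 10% | Rejection, p = 25% |
|---|---|---|---|---|
| 0.1 | 0.1 | 1 point | 5.2% | 5.1% |
| 0.2 | 0.25 | 5 points | 10.5% | 8.0% |
| 0.2 | 0.5 | 10 points | 24.9% | 16.9% |
| 0.3 | 0.5 | 15 points | 44.7% | 31.4% |

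The effect is negligible if home scans are few or shifts are rare, and serious if both are common.

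**The case against.** The home scan is a sensible contingency. It rescues outcomes that would otherwise be missing, it follows phone or home contact, and inclusion criterion 2 already requires parents who can return. On-site experts check all examinations, so a home reading need not stand unreviewed. All of this is fair and is a reason to keep the home scans. It does not restore blinding: the expert check is described as quality control with feedback, the experts' blinding is not stated, and nothing says that their grade sets the outcome.

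A reader might infer three stronger points that the protocol does not support.

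- **That allocation concealment is broken.** The principal investigator has no stated recruiting role. Envelopes are sealed, numbered and opened only after baseline assessments. Concealment would fail only if the sequence reached the enrolling staff. That is possible but not indicated.
- **That home scans are certainly unblinded.** As step 2 shows, knowing the arm needs the link or a cue. The protocol prevents neither, but it does not say that the principal investigator has either.
- **That the 20% dropout allowance gives the number of home scans (16 of 80).** Dropouts are infants lost, whereas home scans recover non-attenders. The allowance is also worded as a minimum, so it sets no upper limit. Likewise, two readings per arm shifted in opposite directions would move the risk difference by 2/40 + 2/40 = 10 points, but that count would be invented.

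**Conclusion.** The concern holds as a conflict within the protocol. The principal investigator's two tasks form an unacknowledged exception to the blinding stated in Section 3.2, and the exception reaches the primary outcome. What is established is the absence of a safeguard, not that readings will be biased. Any bias would plausibly favour the stated hypothesis. Its size is unknown: the 1 to 15 point range depends wholly on the assumed h and e and is not a forecast. The point is worth correcting because the primary outcome is affected and the remedy is cheap.

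**What to change.** 1. Have the independent researcher who creates the sequence also fill and seal the envelopes. This reassigns one clerical task and costs nothing.
2. Keep the home scans. Upload the images under the study ID only, and take the primary-outcome Graf type from a grading of the unmarked images, made blind to arm and to home or clinic setting. Section 3.3 requires two images per hip, one carrying the measured angles, so the grader must not see that one or the operator's values. An existing radiologist or HipScreen expert can do this. It would be a new task: the protocol has the radiologist perform the clinic scans and does not provide for a blinded reading of home images. It concerns only the grade used in the analysis.
3. Blind reading cannot correct the plane or frame chosen by an operator who knows the arm. Report the number of home scans per arm, and add a sensitivity analysis of the primary outcome without them.
4. Amend the blinding statement in Section 3.2 so that it says how home-scanned infants are handled.

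The downside is a few extra image readings for staff already in the trial. No extra visits or equipment are needed.
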